#### **5.4.2. *Temporary halt or early termination***

The trial may be prematurely terminated for safety reasons affecting the risk-benefit balance or if the recruitment of participants cannot be completed within reasonable time. Decisions on premature termination are taken by the sponsor. The Competent Authorities (CA) should be informed as soon as possible via

CTIS, but no later than 15 days after trial suspension.

If the trial is prematurely terminated or suspended, the investigator should immediately inform the participants and ensure appropriate treatment and follow-up.

#### **5.4.3. *End of the clinical trial***

The trial ends when the last participant has completed the last follow-up including the safety follow-up visit six months after revaccination.

## **6. Participant selection**

Participants in the study will be enrolled as part of one of two age categories (60-65 years, and equal or older than 80 years). The goal is to have a similar ratio between male and female participants in both subgroups. Participants from both community dwelling and long-term care facilities will be enrolled in the study. Study participants will be enrolled at two different sites. The younger age group (60-65 years) representing community dwelling individuals will be enrolled at Studieenheteren Akademiskt Specialistcentrum, Region Stockholm. Participants in the older age group (80 years and above) will be enrolled from long-term care facilities at Familjeläkarnas Särskilda boenden (SÄBO).

Adherence to the inclusion criteria as specified in the protocol is essential. Inclusion criteria deviations are not allowed because they can jeopardize the scientific integrity or regulatory acceptability of the study or participant safety. All participants must satisfy all of the following criteria at study entry:

- Male or female individuals who were born between 1965 and 1960 or 1945 and before, who live in the community or in a long-term care facility.
- Individuals who can understand and read Swedish.

- Individuals who can provide written consent and agree (by written consent) to receive the RSV vaccine.
- Participants who, in the opinion of the investigator, can and will comply with the requirements of the protocol.
- Participants who are medically stable in the opinion of the investigator at the time of first vaccination. Participants with chronic stable medical conditions with or without specific treatment, such as diabetes, hypertension or cardiac disease, are allowed to participate in this study if considered by the investigator as medically stable.

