## 1. Synopsis

EU Trial number:	2024-520141-23-01
Title:	Immunogenicity after a prime dose and revaccination with adjuvanted RSVPreF3 vaccine in the most elderly and frail population – an open-labeled phase IIIb trial RSV Immunogenicity Study in the Elderly (RISE)
Trial ID:	RISE
Short background/ Rationale/Aim:	Respiratory syncytial virus (RSV) is a common cause of respiratory tract infections leading to hospitalizations in infants and in elderly. Arexvy is an approved vaccine indicated for the prevention of RSV infections in older adults, however, there is yet limited information on the vaccine's efficacy in individuals $\geq 80$ years old. This study aims to investigate potential differences in the immune responses induced upon vaccination with Arexvy between individuals above 80 years of age and adults 60-65 years old.
Primary objective:	To describe the induction of neutralizing antibodies against RSV A and B following the first dose of Arexvy in older adults aged 80 years and older and those aged 60 to 65 years.
Secondary objectives:	To evaluate the reactogenicity of Arexvy by recording the occurrence of solicited adverse events (AEs) in the study participants. To evaluate the safety of Arexvy in terms of the incidence of unsolicited AEs, SAEs/pIMDs and fatal SAEs.
Primary endpoint:	To assess the neutralizing antibody geometric mean titers (GMTs) against RSV A and B one month after the prime dose (day 31) of Arexvy in study participants aged 60-65 years and $\geq 80$ years old, measured by a neutralization assay. Mean geometric increase (MGI), geometric increase (MGI) between day 0 and day 31 after prime will be calculated (equal to the geometric mean of the individual ratio). A more detailed description can be found in section 10.2.1.

Secondary endpoints:	Occurrence, intensity and duration of solicited AEs in the study participants at the administration site and solicited systemic AEs with an onset during the 4-day follow-up period after each vaccination.  Incidence of unsolicited AEs in the study participants with an onset during the 30-day follow-up period after each vaccination.  Incidence of SAEs or pIMDs in the study participants from the day of vaccination until 6 months.  Occurrence of any fatal SAEs from day 1 up to study end.
----------------------	--

Trial design:	Open-label phase IIIb trial where study participants will be vaccinated at study start and revaccinated 12 months after the first dose. The study period is 18 months.

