### 3. Benefit-risk evaluation

#### ***Expected therapeutic benefits to the individuals participating in the study***

Arexvy is a vaccine already approved by the regulatory authorities in the US (Food and Drug Administration [FDA]) and Europe (European Medicines Agency [EMA]). Arexvy is indicated for adults  $\geq 60$  years of age, and recently also for adults 50-59 years old with underlying conditions increasing the risk for severe disease upon RSV infection (8). In Sweden, RSV vaccination is recommended by the Public Health Agency (Folkhälsomyndigheten) since September 2023 to individuals  $\geq 75$  years of age and to the younger age group  $>60$  years with increased risk of severe RSV-infection. The vaccination coverage is assumed to be overall low in these high-risk groups, although there is no vaccination registration done to confirm this. All participants in this study (grouped in 60-65 years or  $\geq 80$  years age groups) will be offered Arexvy. In previous clinical studies the vaccine showed high protective efficacy. RSV vaccination is especially relevant for the older age group, given that the vaccine is recommended for them by national authorities and since additional knowledge about vaccine immunogenicity in the older group would be beneficial for future recommendations to this population.

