## **4. Trial objectives**

### **4.1. Primary objective**

The primary objective of this study is to describe the induction of neutralizing antibodies following a first dose of Arexvy in older adults aged 80 years and older and those aged 60 to 65 years. We will descriptively compare the neutralizing antibody titers against RSV A and B one month (day 31) after a first dose in both groups.

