#### ***7.1.5. Blinding***

This is an open trial, however each participant who consents to participate in the study will be assigned a unique identification number. This number will be used

to label all study-related data and biological samples to ensure confidentiality. Laboratory testing in this trial will be partially blinded. For laboratory tests carried out by GSK laboratories, data will be collected in an observer-blind manner, only the sample ID and date of the sampling will be made available. The laboratory in charge of the sample testing will be blinded to the intervention assignment. Codes will be used to link the participant and study (without any link to the intervention attributed to the participant) to each sample.

The sponsor's lab personnel will be aware of the specific site in which a sample was obtained and thereby also have knowledge about the respective allocation in an age group.

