#### ***8.1.1. Methods for the primary endpoint***

The primary endpoint of this trial is defined as the descriptive analysis of the differences in RSV A and B neutralizing antibodies at D31 after prime vaccination in the two age groups enrolled in this study. The primary endpoint will be measured in serum by an established neutralization assay. The assays will be performed at accredited laboratories of GSK. The analysis will be performed after the collection of all D31 samples. A short description of the method can be found in section 16.

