### **10.4. *Sample size calculations***

This study is primarily designed to gather descriptive immunogenicity data in older adults upon vaccination with Arexvy, including adults of 80 years of age and older for which data is currently limited. As the study objective is purely descriptive rather than to demonstrate efficacy or test a hypothesis, no formal power-based sample size calculation has been made.

A sample size of 30 individuals in the 60-65 years group and of 35-40 individuals in the 80+ years group was chosen based on feasibility of recruitment, clinical judgement and a 10-20% drop-out expected in the older age group. This sample size of approximately 30 individuals per age group is expected to generate valuable immunogenicity data in an otherwise understudied population and to allow for exploratory comparisons between age groups. Given the descriptive nature of the study, its findings will be interpreted as preliminary.

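### Age group, residence and site coincide, so the day-31 contrast labelled by age compares care-home residents ≥80 with community dwellers 60-65; the birth-year criterion also misses the stated ages

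*Protocol*

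**What the plan says.** Section 6 of the protocol recruits at two sites, one per age group. For the younger group: "The younger age group (60-65 years) representing community dwelling individuals will be enrolled at" one clinic. For the older group: "Participants in the older age group (80 years and above) will be enrolled from long-term care facilities", which form the second site. Section 7.1.5 confirms the arrangement from another direction. It describes the sponsor's laboratory staff as "aware of the specific site in which a sample was obtained and thereby also have knowledge about the respective allocation in an age group".

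The comparison is described by age:
- The Synopsis gives the aim as follows: "investigate potential differences in the immune responses induced upon vaccination with Arexvy between individuals above 80 years of age and adults 60-65 years old".
- Section 4.1 says: "We will descriptively compare the neutralizing antibody titers against RSV A and B one month (day 31) after a first dose in both groups".
- Section 8.1.1 gives the primary endpoint as follows: "descriptive analysis of the differences in RSV A and B neutralizing antibodies at D31 after prime vaccination in the two age groups".
- Section 10.4 expects the sample size "to allow for exploratory comparisons between age groups".

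Section 3 adds that "additional knowledge about vaccine immunogenicity in the older group would be beneficial for future recommendations to this population", where the population is described by age and not by residence.

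The first inclusion criterion (Synopsis and section 6) admits people born 1960-1965, or in 1945 or before, and allows either age group to live in either setting. Section 6 requires every criterion to be met and permits no deviations. Section 7.1.4 places people in an age group as they are found eligible. The stated age categories are 60-65 and ≥80 years.

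**The concern.** **(a) The contrast.** If every older participant lives in long-term care and every younger one in the community, and each group has its own site, a higher or lower day-31 titre in the older group could reflect age, care-home residence or site. A reader of the aim and endpoint would take it as a statement about age and might apply it to people ≥80 living at home, none of whom are planned. The inclusion criterion adds to this. Read alone, it suggests that either age group may be mixed by residence, which the site plan does not provide for.

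**(b) The ages.** Birth years fix the age reached during a calendar year, not the age on the day of entry. People outside the stated categories can therefore be admitted, and some inside them shut out. A 59-year-old without an underlying condition would also sit badly with the indication described in section 3 and with the statement in section 10.5 that the vaccine is used under already approved conditions. This point affects who is admitted. It does not affect how the day-31 contrast reads.

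**Working it through.** **Sample size first.** The only figure that can be reproduced is the older group's enrolment. To keep about 30 (section 10.4) after 10-20% drop-out (section 10.2.2), N = 30/(1 − d). This gives 30/0.90 = 33.3, so 34, and 30/0.80 = 37.5, so 38. Both are within 2 of the stated 35 and 40. The figure is not in dispute.

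**(a) Age against residence.** Planned numbers come from section 10.4 and settings from section 6.

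| | Community | Long-term care |
|---|---|---|
| 60-65 years | 30 | 0 |
| ≥80 years | 0 | 35-40 |

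The total is 65-70, which is everyone planned. Site splits the participants in the same way as residence. A model with an intercept, age group, residence and site has 4 columns. Because the last three columns are identical, its rank is 2, whether the older group has 35 or 40 members. One contrast can be estimated, and it cannot be divided among its three labels by any adjustment.

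**(b) Birth years against age at first dose.** Inputs from the Synopsis are a trial calendar of Q3 2025 to Q2 2027 and about 18 months per participant. First doses can then start on 1 July 2025 and must be given by about 30 June 2027 less 18 months, which is 31 December 2025. Birth dates are assumed uniform over the year.

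Let f be the share of birthdays still to come in 2025 on the dosing date:
- 1 July: 183/365 = 0.501
- 1 October: 91/365 = 0.249
- 31 December: 0

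The younger group is drawn from six birth years (1960-1965), so the expected number of 59-year-olds among 30 is 30 × f/6. The completed ages 60-65 also span six years of birth. The share of that age range shut out because they were born in 1959 and are still 65 is therefore f/6. The chance that an enrolled person born in 1945 is still 79 is f.

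| First dose (2025) | Aged 59 among 30 | 60-65s shut out | 1945-born still 79 |
|---|---|---|---|
| 1 July | 30 × 0.501/6 = 2.5 | 0.501/6 = 8.4% | 50% |
| 1 October | 30 × 0.249/6 = 1.2 | 0.249/6 = 4.2% | 25% |
| 31 December | 0 | 0% | 0% |

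The protocol does not say how many participants will have been born in 1945, so no count of 79-year-olds can be given. If first doses slipped into 2026, the mismatch would reverse: people born in 1960 could be 66, and people born in 1946 who had turned 80 would be shut out.

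**The case against.** The strongest reply to (a) is that the protocol is open about whom it enrols and claims little. Its title refers to the most elderly and frail, section 2 names frail people as part of the evidence gap, and section 6 states the settings plainly. The sentence in section 8.1.1 goes on to limit the comparison to the groups enrolled in the trial. Sections 10.2.1 and 10.4 call the study exploratory, descriptive and preliminary, and nowhere does the protocol attribute a difference to age. Frailty is recorded on the Clinical Frailty Scale (section 5.2). Neutralisation is run by laboratories that see only sample ID and sampling date (section 7.1.5), which weakens site as a rival explanation. Fold rise and sero-response are measured against each person's own baseline. A broad criterion beside a narrower recruitment plan need not be a contradiction, and section 6's sentence about enrolling from both settings is true of the trial as a whole.

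Much of this stands. No false inference is written down, assay bias linked to site is unlikely for the primary endpoint, and frailty can be described. But neither the title nor the words about enrolled groups restate the aim or endpoint by residence. A frailty score cannot separate two variables that never vary apart, and the response to vaccination may itself differ by residence. Calling a study descriptive concerns testing and precision; a description still has to name correctly the groups it compares.

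On (b), the birth years do match age attained in 2025. Read together with the age categories, a 59- or 79-year-old has no group to enter. The 1 July figure is also an extreme, since version 2.0 is dated 12 June 2025 and approval must come first. That is fair, and it is why the point is minor. But the mandatory criterion is the birth year, and the text does not say which definition prevails.

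**Conclusion.** Both parts hold.

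**(a)** This is the substantive part. With 30 and 35-40 participants in two of the four cells and none in the other two, the day-31 difference contrasts long-term-care residents aged ≥80 with community-dwelling adults aged 60-65. It cannot be attributed to age or carried over to people ≥80 in the community. This follows from the enrolment plan alone, needs no assumption about titres, and cannot be repaired in an analysis plan. It limits what may be concluded and does not invalidate the data: the geometric mean titres, geometric mean increases and sero-response rates within each group are unaffected. No size of bias in any titre is claimed.

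**(b)** This is an edge effect of under six months of age for entry in July-December 2025. It amounts to between 2.5 and 0 expected 59-year-olds among 30, with 8.4% to 0% of people aged 60-65 shut out. It rests on uniform birth dates and on the dosing window inferred from the trial calendar.

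The wording should be corrected before the day-31 results are reported.

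**What to change.** **(a)** Word the aim, primary objective, primary endpoint and conclusions as a contrast of long-term-care residents aged ≥80 years with community-dwelling adults aged 60-65 years. State that age, residence and site cannot be separated in this trial. Bring the residence part of the inclusion criterion (Synopsis and section 6) into line with the site plan; if only the objective is relabelled, the two will conflict. Sites and numbers stay as they are.

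**(b)** Reconcile the birth-year criterion with the age categories in the Synopsis and section 6, and with sections 3 and 10.5, for example by defining eligibility on one stated age basis at first vaccination.

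**Cost:** wording changes in a protocol amendment, covering the aim, objective, endpoint, interpretation and one inclusion criterion. If they are judged substantial, section 13 requires permission through CTIS before they are used. No extra participants, visits or samples are needed.

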Trial population:	Adults 60-65 years old and ≥80 years old.
Number of participants:	30 adults in the 60-65 years age group and 35-40 adults in the ≥80 years age group.
Inclusion criteria:	
Male or female individuals who were born between 1965 and 1960 or 1945 and before, who live in the community or in a long-term care facility.
 
Individuals who can understand and read Swedish.
 
Individuals who can provide written consent and agree (by written consent) to receive the Arexvy vaccine.
 
Participants who, in the opinion of the investigator, can and will comply with the requirements of the protocol.
 
Participants who are medically stable in the opinion of the investigator at the time of first vaccination.
 
Participants with chronic stable medical conditions with or without specific treatment, such as diabetes, hypertension or cardiac disease, are allowed to participate if considered by the investigator as medically stable.

Exclusion criteria:	
Individuals who are medically immunocompromised, less than 2 years since hematopoietic stem cell transplantation (HSCT) or graft-versus-host disease (GVHD), solid-organ transplanted, using immunosuppressive drugs for treatment of cancer and who have inflammatory mediated or autoimmune conditions, as judged by the Investigator.
 
Individuals who have already received an RSV vaccine dose at any time in the past.
 
Any known or suspected reaction, hypersensitivity or allergies to be exacerbated by any product or component included in the vaccine and trial.
 
Mental inability, reluctance or language difficulties that result in difficulty understanding the meaning of participation in the trial.
 
Treatment or disease which, according to the

investigator, can affect treatment or trial results.

Any of the following medical conditions:

- Unstable chronic illness
- Recurrent or un-controlled neurological disorders or seizures
- Significant underlying illness that in the opinion of the investigator would be expected to prevent completion of the study
- Any other medical condition that in the judgment of the investigator would make intramuscular injection unsafe
- Any other clinical condition that, in the opinion of the investigator, might pose additional risk to the participant due to participation in the study

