- Any history of dementia or any medical condition that moderately or severely impairs cognition and understanding of the informed consent form and/or study procedures
- History of chronic alcohol consumption and/or drug abuse as deemed by the investigator to render the potential participant unable/unlikely to provide accurate safety reports or comply with study procedures.

Planned move during the study period that will prohibit participating in the study until study end.

Participation of any study personnel or their immediate dependents, family or household members as well as any family relations to Sponsor or PI.

Co-administration of other vaccines less than 14 days before or after study vaccination. A period of less than 30 days before or after study vaccination applies in the case of Shingrix.

Intervention:	Study participants will be vaccinated at study start and revaccinated 12 months after. The study period is approximately 18 months per study participant, during which 10 blood draws are planned.
Investigational medicinal product(s),	Adjuvanted RSVPreF3 vaccine (trade name Arexvy, manufactured by GSK). Arexvy is a sterile injectable suspension for intramuscular use (0.5 mL) containing

dosage, administration:	120 µg of recombinant RSVPreF3 adjuvanted with AS01E.
Ethical considerations, benefit/risk:	All study participants (60-65 years old and ≥80 years old) will be given Arexvy, an approved vaccine specifically indicated for preventing severe respiratory tract disease in this population. Arexvy has demonstrated a high protective efficacy, and an acceptable reactogenicity and safety profile. The overall benefit/risk balance is positive.
Planned duration of the trial:	Q3 2025 – Q2 2027

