#### **4.6. Exploratory endpoint(s)**

## 5. Trial design and procedure

### 5.1. Overall trial design

[figure not shown]
This is a phase IIIb open-label post-marketing clinical trial using an already approved vaccine in the targeted population group. The design will generate immu[REDACTED]

and maintenance of RSV vaccine-induced immunity in the oldest vaccine recipients. The study includes a prime vaccination and revaccination after one year. [REDACTED]

[REDACTED] The study period is approximately 18 months per study participant. After screening and Informed Consent procedure, 10 visits are planned where one prime dose of vaccine Arexvy (GSK) 0.5 mL i.m is given at the first visit (V1) and a revaccination at the 12-month timepoint (V7). The design and scheduled activities are shown in Figure

1 and Table 1.

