### **5.4. Start, end, temporary halt and early termination**

#### **5.4.1. *Start of the clinical trial***

The start of the trial is defined as the start of screening activities. Sponsor will report the start of the trial in Sweden through notification in the Clinical Trial Information System (CTIS) within 15 days.

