## **6.2. Screening and inclusion**

Participant eligibility (that participants fulfil all inclusion criteria and do not meet any exclusion criteria) is established at baseline visit before visit 1, or if these two visits are at the same time, before deciding to give the first dose of the study vaccine.

Study vaccine administration may be postponed within the permitted timeframe for each study vaccination if a possible candidate cannot receive the vaccine at the baseline visit. Vaccination can be delayed for 10 days in case of:

- Acute disease and/or fever at the time of vaccination. Fever is defined as a temperature  $\geq 38.0^{\circ}\text{C}/100.4^{\circ}\text{F}$  by any route. The route for measuring temperature can be oral, axillary or tympanic.

Participants with a minor illness (such as mild diarrhea, mild upper respiratory infection) without fever may be vaccinated at the discretion of the investigator.

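### The birth-year inclusion criterion does not deliver the stated age groups (60-65; 80 or older) at study entry

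*Protocol*

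**What the plan says.** The Synopsis gives the trial population as "Adults 60-65 years old and ≥80 years old". Section 6 opens in the same terms: participants are "enrolled as part of one of two age categories (60-65 years, and equal or older than 80 years".

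The inclusion list tests age in one line only, worded alike in the Synopsis and section 6: "Male or female individuals who were born between 1965 and 1960 or 1945 and before". Section 6 introduces the list with "All participants must satisfy all of the following criteria at study entry" and permits no deviations from it. Section 6.2 says when this is checked: "Participant eligibility (that participants fulfil all inclusion criteria and do not meet any exclusion criteria) is established at baseline visit before visit 1" (or, if the two visits coincide, before the decision to give the first dose).

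No enrolment dates are given. The Synopsis gives the planned duration as "Q3 2025 – Q2 2027". Section 5.4.1 adds "The start of the trial is defined as the start of screening activities", and section 5.1 adds "The study period is approximately 18 months per study participant".

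**The concern.** The groups are defined by age and eligibility by calendar year of birth. The two agree only if age means the age reached during 2025, a convention the protocol never states and one that fits poorly with criteria to be met at entry. A site that follows the list will enrol some people outside the stated population and turn away some inside it. Because deviations are not allowed, it cannot correct this by judgement.

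Beyond labelling, the consequence concerns the indication. Section 3 describes the vaccine as indicated from 60 years, and at 50-59 years only with conditions that raise the risk of severe RSV disease. No inclusion criterion asks for such a condition, so a 59-year-old without one could be admitted. Yet the benefit/risk statement in the Synopsis treats every participant as belonging to one of the two age bands and as covered by the indication, and section 10.5 relies on use within the approved terms. These passages must be reconciled.

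**Working it through.** **Entry window (inferred).** The earliest start is the first day of Q3 2025, 1 July 2025; the latest start still in Q3 is 30 September. The end of Q2 2027 is 30 June 2027. Taking off 18 months gives a latest first vaccination of about 30 December 2025.

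**Admitted birth dates.** Reading the range as inclusive, 1960-1965 holds 6 × 365 + 2 leap days = 2192 dates. The older group is 1945 and before.

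**Single entry days.** Completed age was computed for every birth date.

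| Entry day | Admitted, aged 59 | Admitted, aged 79 | Aged 65 but excluded (born 1959) |
|---|---|---|---|
| 1 Jul 2025 | 183 dates (8.3% of 2192) | 183 | 183 |
| 1 Oct 2025 | 91 (4.2%) | 91 | 91 |
| 15 Nov 2025 | 46 (2.1%) | 46 | 46 |
| 30 Dec 2025 | 1 | 1 | 1 |
| 31 Dec 2025 | 0 | 0 | 0 |

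Within 2025 the rule matches the stated bands only on 31 December.

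**Average over the window.** Birth dates and entry days are assumed uniform. The count falls by one per day, so over N days ending on 30 December the mean is (N + 1)/2.

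- Start 1 July, N = 183: mean (183 + 1)/2 = 92.0. Aged 59: 92.0/2192 = 4.2%; × 30 = 1.26 participants.
- Start 30 September, N = 92: mean (92 + 1)/2 = 46.5. Aged 59: 46.5/2192 = 2.1%; × 30 = 0.64 participants.
- Excluded 65-year-olds: the same 92.0 and 46.5 dates. The completed-age 60-65 band also holds 2192 dates, so this is 4.2% and 2.1% of it.

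**Older group.** Of 1945 births, 92.0/365 = 25.2% (1 July start) or 46.5/365 = 12.7% (30 September start) would be 79. The share of the older group born in 1945 is not in the protocol. Assuming 5-15% of 35-40 participants:

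- 1 July start: 35 × 0.05 × 0.2521 = 0.44 to 40 × 0.15 × 0.2521 = 1.51.
- 30 September start: 35 × 0.05 × 0.1274 = 0.22 to 40 × 0.15 × 0.1274 = 0.76.

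**If entry slips into January-March 2026.** Nobody is 59 or 79, but the error reverses. On average 2.1% of the younger group is aged 66 (0.0209 × 30 = 0.63). People born early in 1946 are already 80 yet excluded: 90 birth dates by 31 March 2026.

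**Exclusive reading of the range (1961-1964).** Nobody aged 59 is admitted, but every 65-year-old is excluded throughout 2025 and the 79-year-olds are still admitted. This reading does not remove the conflict.

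**Group allocation.** Birth years 1946-1959 lie between the bands, a gap of 14, and section 6 gives each group its own site. Nobody can be put in the wrong group.

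**The case against.** The strongest reply is that section 6 should be read as a whole. Its opening sentence names the age bands, and an investigator who applies both that sentence and the list would enrol nobody aged 59 or 79. That is a possible reading, but it does not resolve the matter: 65-year-olds born in 1959 remain excluded although they are in the stated band, and the list is what participants must satisfy.

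A second reply is that the convention is recognisable: 2025 minus 60, 65 and 80 gives 1965, 1960 and 1945 exactly. This is probably what was intended. It is not stated, and even if it were, the 59-year-olds would remain and the indication passages would still need reconciling.

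Several points on size stand. The larger figures need screening to begin on the first day of Q3, although version 2.0 is dated 12 June 2025 and section 12.2 requires approval first. The 5-15% share born in 1945 has no support in the protocol. Only those 59-year-olds without a risk condition fall outside the quoted indication, so that number is below 0.6-1.3 by an unknown amount and may be zero. In 2025 nobody admitted is a full year below the stated lower limit, and section 10.4 already calls the findings preliminary. These points limit the consequences; they do not make the two definitions agree.

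**Conclusion.** The concern holds, as a minor point. On every entry day from 1 July to 30 December 2025 the eligibility rule, read inclusively, defines a population different from the stated one. About 0.6-1.3 of the 30 younger participants would be expected to be 59, and an equal share of the 60-65 band (2.1-4.2%) is shut out. The older group might include 0.2-1.5 people aged 79, a range that depends on the assumed 1945-born share. The figures also rest on the inferred entry window and on uniform birth and entry dates; that a mismatch exists does not depend on uniformity. The effect on the descriptive GMT comparison is small. What matters is a clean eligibility rule and consistency with the protocol's own statements on population and indication.

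**What to change.** In the Synopsis and in section 6, replace the birth years with completed age on the day of first vaccination (V1), using the two bands the protocol already states: 60-65 years, and 80 years or older. Naming V1 also settles the reference day, since V1 may follow the baseline visit by up to 10 days. This removes the mismatch on any entry date, including in 2026. Merely stating the age-reached-in-2025 convention would make the rule clear, but would leave the benefit/risk statement in the Synopsis, section 3 and section 10.5 to be reconciled with the admission of 59-year-olds.

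The cost is one line in two places, with a protocol amendment under section 13 if the change is judged substantial. A few candidates just below 60 or 80 would wait for their birthday or become ineligible, and a few 65-year-olds born in 1959 would become eligible.
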